11.2 Data Management

The primary source data for the study will be maintained by NIH Clinical Research Information System (CRIS) and the NIH Clinical Trials Database (CTDB), with subject surveys and interval questionnaires administered by the secure Clinical Trials Survey System (CTSS). Study data and outcomes will be monitored by a Data Safety Monitoring Committee (DSMC) consisting of NIH staff not affiliated with the study who will meet every 6 months and review un-blinded data. Possible adverse outcomes of treatment will be as per NIH and GCP monitoring guidelines. An IND waiver request was granted by FDA for this study.

11.3 Study Timeline

Table 4: Study Timeline

Time Period	Year 1		Year 2		Year 3		Year 4		Year 5	
	Q 1/2	Q 3/4	Q 1/2	Q 3/4	Q 1/2	Q 3/4	Q 1/2	Q 3/4	Q 1/2	Q 3/4
Finalize Protocol CRFs	X									
Submit IRB	X									
Finalize SOPs	X									
Build Database	X	X								
Pilot Test CRFs and Database	X	X								
Recruit Participants		X	X	X	X	X	X	X		
Conduct Study Visits				X	X	X	X	X		
Interim Analysis					X		X			
DSMC Reviews		X	X	X	X	X	X	X	X	X
Clean Data and Lock Database									X	
Analysis and Publication										X

12 HUMAN SUBJECT PROTECTION ISSUES

12.1 Selection

12.1.1 *Human Participants Involvement and Characteristics*

For the purposes of this study, human participants will undergo physical examination and questionnaire completion, CAVI, Endopat, FDG PET CT and DXA scan (a subset of subjects), blood draws, Echocardiogram, and exposure to study drug (pioglitazone and placebo). There will be no involvement of fetuses, neonates, children, pregnant women, prisoners, or institutionalized individuals. Women of childbearing potential will be included, but risk reduction measures (including required contraception and pregnancy testing) are in place to protect them.

12.1.2 *Inclusion of Women, Minorities, and Children:*

12.1.2.1 Women

Women and men with SLE will be recruited into this study. Research consistently shows that women are 7-10 times more likely to develop SLE than men. For this reason, we expect approximately 80-90% of participants to be female. Based on the past record of the investigative team and the SLE natural history protocol, we believe specialized outreach for the recruitment of women will not be necessary.

12.1.2.2 Inclusion of Minorities

No ethnic groups will be excluded from this protocol. All participants must have a diagnosis of SLE. Research reviews indicate an increased risk for SLE development in African-Americans and Hispanics. Targeted enrollment rates will be based on data from the natural history protocol of SLE at NIH. Based on the past record of the investigative team, we expect that minorities will be recruited in adequate numbers. However, the PI will monitor recruitment progress on an annual basis, and will implement outreach strategies if enrollment falls short of targets. Outreach strategies include recruiting participants from physician offices in the area that service a predominance of minority patients.

12.1.2.3 Inclusion of Children

Children will be excluded from this study as pioglitazone is not approved in children and the proposed vascular tests have not been validated in children.

12.1.2.3 Inclusion of NIH employees

NIH employees are allowed to participate if they fulfill criteria. NIH employees who become subjects will be protected, as specified in SOP14F

12.2 **Benefits and Risks/Discomforts**

12.2.1 *Benefits*

The knowledge to be gained may result in better, more focused treatment approaches, implemented earlier in the course of disease, to reduce cardiovascular morbidity and mortality associated with SLE and other inflammatory autoimmune diseases. This would directly benefit future patients and greatly improve our understanding of these debilitating comorbidities.

This study will provide important preliminary information about the effect of PPAR pathways in SLE patients and may contribute to a better understanding of the pathophysiology of SLE. Patients will benefit from comprehensive clinical exams and laboratory tests during the trial, as well as assessment of CV risk and thorough evaluation by experts in SLE. Otherwise, there may be no direct benefits to participants. The study agent is not expected to be associated with the most common toxicities of therapies commonly used in the treatment of SLE, such as severe immunosuppression, myelosuppression, or amenorrhea. This study involves more than minimal risk.

12.2.2 *Potential Risks*

12.2.2.1 Blood Draws

The risks of venous puncture include the occurrence of discomfort and/or bruising at the site of puncture. Less commonly, there may be formation of a small blood clot or swelling of the surrounding area as well as bleeding from the puncture site. Syncope and local infection may occur. These are minor risks.

12.2.2.2 Physical Exam and Questionnaire-based Data Collection

Some participants may experience discomfort or frustration these procedures. However, the risks for the participants are felt to be similar to those encountered in a standard physical examination. Breach of confidentiality and the possible discomfort associated with being asked personal questions about health history and the completion of questionnaires pose minimal risks. Risks due to physical exam and questionnaire-based data collection are considered negligible.

12.2.2.3 Vascular Function Studies

No complications are expected from these procedures. Minor discomfort from the use of blood pressure cuffs may be experienced and is similar to having one's blood pressure checked.

12.2.2.4 FDG/PET/CT

The NIH Clinical Center PET department uses only commercially available FDG.

The effective radiation dose from 10 mCi FDG is approximately 0.62 rem. Thus the total radiation from one FDG scan and a transmission CT scan is 1.32 rem. In addition to any radiation concern, there could be psychological distress caused by an incidental finding of asymmetric FDG uptake that would likely necessitate additional investigation to exclude cancer or other lesions (see below).

Additional minimal risks include bleeding or bruising at the venous site of FDG administration. We have provided radiation dosimetry at the end of this protocol. This procedure will not be performed more often than twice per patient during the 8 month duration of this trial and will be performed in 30 out of the 70 patients. Overall, minimum exposure will be 0 rem/year (only

vascular function tests but no imaging) and maximum exposure will be 2.64 rem/year, which is within the annual exposure limits.

Participants may experience mild claustrophobia from the PET CT. The participant will be able to notify the technician throughout the scan if he/she needs to come out of the scanner.

12.2.2.5 Incidental Findings

Incidental findings from imaging studies of coronary disease, obstructive or non-obstructive, will be reported to the subject's referring physician. This protocol will follow the NIH Clinical Center Guidelines for Management of Small Pulmonary Nodules Detected on CT Scans. The literature has noted incidental findings on PET/CT scans to include neoplastic and non-neoplastic lesions. We have broadened our findings to include non-neoplastic and also inflammatory lesions such as lymph nodes as well as solitary pulmonary nodules. Neoplastic findings include cancer of the colon, lung and soft tissue (sarcoma); however, except for lung cancer, these other 2 cancer types have not been highly detected by PET/CT. Information regarding incidental findings is explained in the informed consent to help the subjects understand that these findings will be included on their report, sent to their physician, and may require clinical testing as a follow up to define the abnormality. Prior to sending report, the investigators will provide dedicated follow up time with subjects to inform them of findings and as needed, will provide consult with appropriate medical personnel.

12.2.2.6 Study Drug

Participants will be randomized to pioglitazone or placebo and all patients will at some point receive pioglitazone given the crossover nature of trial. Risks of pioglitazone use in this population (i.e. non-diabetic) are as follows:

- Decreases in hemoglobin and hematocrit of 2-4%. These reductions may be due to an increase in plasma volume and usually pose only minor risk. CBC will be monitored on all patients at each study visit.
- Mild to moderate edema. Pioglitazone is contraindicated in patients with NYHA Class III or IV cardiac failure. In diabetics, concern over the use of rosiglitazone and worsening CV outcomes is still a matter of debate but a black box has been included in the medication guide describing a risk for congestive heart failure exacerbation in individuals taking TZDs. For our study, all patients will undergo a baseline echocardiogram and will be excluded for an ejection fraction <45% and/or evidence of NYHA class II-IV.
- Hepatic effects. Pioglitazone can cause decreases in hemoglobin and hematocrit of 2-4%. These reductions may be due to an increase in plasma volume and usually pose only minor risk. While pioglitazone is typically not associated with hepatic toxicity or liver function test (LFT) elevations, the pioglitazone package insert states there are post marketing reports of hepatic failure and that causality cannot be excluded; Medwatch report states there is an association with hepatitis, hepatic enzyme elevations to 3 or more times the upper limit of normal. Pioglitazone is structurally related to troglitazone

(no longer marketed), which has been associated with idiosyncratic hepatotoxicity and rare cases of liver failure, liver transplants, and death. In a recent study of non-diabetics treated with pioglitazone for similar periods of time to what is proposed for our study, no changes in LFTs were observed⁶⁸. Similarly, in our RA study, we did not detect any significant LFT abnormalities, even in those patients concomitantly taking methotrexate. Nevertheless, LFTs will be monitored on all patients at each study visit and those patients with LFTs >2x upper limit at Screening visit will be excluded. If during the trial, LFTs increase to > than 3x fold the upper limit of normal (ULN), levels will be rechecked within 36 hours and if elevation >3 ULN persists and there are not alternative etiologies, therapy will be discontinued. If LFTs are elevated >2 but \leq 3x ULN (after confirming within 48 hours), we will investigate etiology of liver enzyme elevation and cautiously reinstate therapy if alternative etiology is found. For patients with NAFLD that are enrolled, based on recent clinical trials that have been published (Cusi K et al. Annals of Internal Medicine 2016) assessing the role of long-term pioglitazone treatment for nonalcoholic steatohepatitis, we will include only patients that have LFTs < 3 times ULN. If there is an increase to \geq 3 times ULN once study drug starts during monitoring (confirmed within 24 hours), drug will be stopped.

- Interaction with hormonal contraceptives may reduce the effectiveness of hormonal contraception. Patients will be required to also use a barrier method during the trial if they are taking oral contraceptives.
- The most common side effects reported were upper respiratory tract infection, sinusitis, pharyngitis, headache, myalgia, and tooth disorder.
- Very rarely, pioglitazone may be associated with sporadic, transient elevations in CPK levels, which have been self-resolving.
- Small weight gains (<5 kg) are associated with pioglitazone use, usually with more prolonged use than the treatment course we are proposing. Weight and edema will be monitored closely and patients will be instructed to notify investigators if weight is gained or edema or dyspnea develop.
- An increased incidence of bone fracture was noted in female patients taking TZDs. During a mean follow-up of 34.5 months, the incidence of bone fracture in females was 5.1% (44/870) for pioglitazone versus 2.5% (23/905) for placebo. This difference was noted after the first year of treatment and remained during the course of the study. No increase in fracture rates was observed in men treated with pioglitazone 1.7% (30/1735) versus placebo 2.1% (37/1728). Given the short duration of the trial, we will not assess the effect of this drug on bone metabolism. Given that the mechanism of bone fractures with TZDs is considered different than the one associated with corticosteroid use, we will not change inclusion/exclusion criteria based on medication use. In female patients, attention will be given to assessing and maintaining bone health according to current standards of care and in communication with treating rheumatologist. As mentioned in the exclusion criteria, we will exclude postmenopausal women who have a DXA scan showing a T score worse than -2.5, unless they are willing to begin a bisphosphonate by visit day 1.
- As mentioned above, there have been data suggesting an increase in bladder cancer in diabetics that have been on TZDs for > 2 years. Given the short duration of this trial, no significant concerns are present. Nevertheless, we will exclude patients who have received cyclophosphamide over the last year, whoever developed hemorrhagic cystitis,

or those with a previous history of bladder cancer, or with a history of hematuria not explained by another cause.

Overall, given the short duration of exposure to pioglitazone (3 months), we do not expect repercussions on bone health, bladder or adverse CV outcomes.

12.2.2.7 Echocardiogram:

No side effects are associated with echocardiogram.

12.2.2.8 DXA scan:

The exposure to radiation is minimal from this procedure. No side effects are otherwise expected and this will only be performed in postmenopausal subjects that have not undergone a DXA scan over the last year.

12.3 ADVERSE EVENT AND UNANTICIPATED PROBLEM REPORTING:

The Principal Investigator will be responsible for detecting, documenting, and reporting AEs and SAEs in accordance with the protocol, IRB requirements, and federal regulations.

12.3.1 Definitions:

12.3.2 Adverse Event:

An adverse event (AE) is any unfavorable and unintended diagnosis, symptom, sign (including an abnormal laboratory finding), syndrome, or disease that either occurs during the study, having been absent at baseline, or if present at baseline, appears to worsen. All AEs will be graded for intensity (severity) and relationship to study drug.

12.3.3 Unanticipated Problem:

The Office for Human Research Protections considers unanticipated problems to be any incident, experience, or outcome that meets all of the following criteria:

- Is unexpected in terms of nature, severity, or frequency given a) the research procedures that are described in the IRB-approved research protocol and informed consent, and b) the characteristics of the subject population being studied;
- Is related or possibly related to participation in the research (possibly related means there is a reasonable possibility that the incident, experience, or outcome may have been caused by the procedures involved in the research); and
- Places subjects or others at a greater risk for physical, psychological, economic, or social harm than was previously known or recognized.

An incident, experience, or outcome that meets the 3 criteria above will generally warrant consideration of substantive changes in order to protect the safety, welfare, or rights of subjects or others. Examples of corrective actions or substantive changes that might need to be considered in response to an unanticipated problem include the following:

- Changes to the research protocol initiated by the investigator prior to obtaining IRB approval to eliminate apparent immediate hazards to subjects.
- Modification of inclusion or exclusion criteria to mitigate the newly identified risks.
- Implementation of additional procedures for monitoring subjects.
- Suspension of enrollment of new subjects.
- Suspension of research procedures in currently enrolled subjects.
- Modification of informed consent documents to include a description of newly recognized risks.
- Provision of additional information about newly recognized risks to previously enrolled subjects.

Per the definition, only a subset of AEs would be further characterized as unanticipated problems. Additionally, there are other sorts of events that, while not AEs, would also be characterized as unanticipated problems (e.g., contaminated study drug).

12.3.4 Serious Adverse Event:

A serious adverse event (SAE) is defined as any untoward medical occurrence that:

- Results in death,
- Is life-threatening (defined as a subject at immediate risk of death at the time of the event; it does not apply to an AE which hypothetically might have caused the death if it were more severe),
- Requires or prolongs hospitalization (i.e. the AE required at least a 24-hour inpatient hospitalization or prolonged a hospitalization beyond the expected length of stay; hospitalizations for elective medical/surgical procedures, scheduled treatments, or routine check-ups are not SAEs by this criterion),
- Results in a congenital anomaly or birth defect (i.e., an adverse outcome in a child or fetus of a patient exposed to the trial drug prior to conception or during pregnancy),
- Causes a persistent or significant disability/incapacity (i.e. the AE resulted in a substantial disruption of the patient's ability to carry out normal life functions), or

- Is any other condition that, in the judgment of the investigator, represents a significant hazard or it does not meet any of the above serious criteria but may jeopardize the patient and may require medical or surgical intervention to prevent one of the outcomes listed above.

12.3.5 Medical Events Not Qualifying as Adverse Events or Serious Adverse Events:

Signs and symptoms of pre-existing medical conditions will not be recorded or reported as AEs or SAEs, unless they represent a clinically significant change from the baseline disease status documented at the Pre-screening Visit. In addition, hospitalization for elective procedures or surgeries will not be considered SAEs, nor will inpatient hospitalizations for convenience.

12.3.6 Clinical Laboratory Test Results Not Qualifying as Adverse Events or Serious Adverse Events:

A clinically significant laboratory result that is present at baseline and does not change significantly during the study will not be reported as an AE or SAE. The clinical significance of a change in a laboratory result will be determined by the investigator.

The Principal Investigator or designated AI will evaluate all clinical laboratory and imaging results for clinically significant abnormalities and document the evaluation in the medical record and case report form. A laboratory abnormality will be documented as an adverse event using the following criteria:

- The abnormality is not already encompassed by a reported adverse event (e.g., elevated AST need not be reported as an AE if Liver Failure has already been reported as an AE).
- The abnormality is considered clinically significant by the Investigator.

Clinically significant lab abnormality is defined as meeting the following:

- Necessitates study drug dosing modification (i.e., dose reduction, interruption or discontinuation); and/or
- Requires a therapeutic intervention (e.g., concomitant medication, blood transfusion or dialysis); and
- Is unexplainable by the patient's current and past medical conditions

The Principal Investigator will follow significant abnormalities until they return to baseline or stabilize.

12.3.7 Lupus Flare:

A lupus flare is any significant worsening of the signs, symptoms and laboratory test abnormalities associated with lupus. Any increase in the SLEDAI 2K index of 3 or more will be considered as a SLE flare.

12.3.8 Reporting of Adverse Events, Unanticipated Problems and Protocol Deviations:

12.3.8.1 Intensity of Adverse Event:

The intensity (severity) of AEs and SAEs will be graded according to a descriptive scale based on the National Cancer Institute Common Terminology Criteria for Adverse Events (CTCAE), Version 4.0. If AEs and SAEs is not available at CTCAE, it will be graded according to below chart.

Severity Definitions

Grade	Definition
1. Mild:	Causing no limitation of usual activity
2. Moderate:	Causing some limitations of usual activities
3. Severe:	Causing inability to carry out usual activities
4. Life Threatening:	Patient was at immediate risk of death from the event

For lupus flares, we will use the following criteria based on validated activity scores: (changes are points increased compared to baseline visit)

Increase in SLEDAI 2K: 2-4: Mild

Increase in SLEDAI2K: 5-8: Moderate

Increase in SLEDAI 2K: > 9: Severe

12.3.8.2 Relationship to Study Drug and Procedures:

For all AEs and SAEs, the investigator will provide his/her best estimate of the causal relationship between the event and study drug, and the causal relationship between the event and study procedures. The degree of certainty about causality will be graded according to the criteria in Table. 5.

Table 5. Relatedness of Adverse Event to Intervention

Causality	Description
Not Related Category	
Unknown	Not enough information exists for the assessment of causality at the time of occurrence.
Unrelated	Adverse event is clearly due to extraneous causes (e.g., underlying disease, environment)
Related Category	
Unlikely (must have at least 2)	
 1) does not have temporal relationship to intervention 2) could readily have been produced by the subject's clinical state 3) could have been due to environmental or other interventions 4) does not follow a known pattern of response to intervention 5) does not reappear or worsen with reintroduction of intervention
Possible (must have at least 2)	
 1) has a reasonable temporal relationship to intervention 2) could not readily have been produced by the subject's clinical state 3) could not readily have been due to environmental or other interventions 4) follows a known pattern of response to intervention
Probable (must have at least 3)	
 1) has a reasonable temporal relationship to intervention 2) could not readily have been produced by the subject's clinical state or have been due to environmental or other interventions 3) follows a known pattern of response to intervention 4) disappears or decreases with reduction in dose or cessation of intervention
Definite (must have all 4)	
 1) has a reasonable temporal relationship to intervention 2) could not readily have been produced by the subject's clinical state or have been due to environmental or other interventions 3) follows a known pattern of response to intervention 4) disappears or decreases with cessation of intervention and recurs with re-exposure

12.3.8.3 Expectedness of Adverse Events:

For purposes of regulatory reporting, the medically responsible investigator will determine whether an AE or SAE is expected or unexpected. Expected adverse events are those adverse events that are listed or characterized in the Package Insert or in the Physicians' Desk Reference.

Unexpected adverse events are those not listed in the Package Insert (P.I.) or Physicians' Desk Reference (PDR), published medical literature, protocol, and informed consent document or not identified. This includes adverse events for which the specificity or severity is not consistent with the description in the P.I., PDR, published medical literature, protocol and informed consent. For example, under this definition, hepatic necrosis would be unexpected if the P.I. only referred to elevated hepatic enzymes or hepatitis.

For consistency of labeling and categorizing adverse events, the NCI CTCAE, Version 4.0 will be used in this study.

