9.2 Inclusion Criteria

1. For females and males 18 years old or older: females should be on adequate contraception if they are of child-bearing potential, which should be documented by a clinician, unless patients or their spouse/partner(s) have previously undergone a sterilization procedure. Adequate contraception will be considered:
 - Intrauterine device (IUD),
 - Hormone implants,
 - Injectable contraceptives,
 - Oral contraceptives plus a barrier method (male condom, female condom or diaphragm),
 - Abstinence, or
 - A vasectomized partner.
2. Meet revised ACR criteria and 2012 SLICC criteria for SLE and have: a) a baseline SLEDAI-2K ≥ 4 and <20 or a clinical SLEDAI-2K ≥ 2 (not considering anti-dsDNA or complement levels) and b) lack of BILAG A flare at baseline (See Appendix 3).
3. Stable doses of immunosuppressants and/or antimalarials for at least 3 months, and/or corticosteroids for at least 2 weeks. The prednisone dose may be increased after screening visit as long as the total dose is less than 20 mg of prednisone or equivalent per day and the subject is on stable dose for at least 2 weeks prior to their Day 1 visit. If on statins, should have been on stable doses for at least 6 months.
4. Allowed concomitant lupus-related medications
Antimalarials,
Prednisone ≤ 20 mg daily or equivalent doses of other corticosteroids;
Immunosuppressants:

Mycophenolate mofetil, up to 3000 mg/day,

Methotrexate, up to 30 mg/week,

Azathioprine, up to 3 mg/kg/day,

Leflunomide, up to 20 mg/day,

Cyclosporine, up to 5 mg/kg/day

Tacrolimus, up to 0.1 mg/kg/day

NSAIDs and aspirin

Note: While it would be highly desirable to maintain corticosteroid dosage at constant level for trial duration, it is impractical to anticipate that all patients with active SLE can be maintained without therapy modification for an 8-month period. Because corticosteroids are acceptable agents for treatment of the vast majority of minor lupus flares, and patients with major flares (BILAG 2004 A or recent change in medications) will be excluded, this will provide standardized treatment across study population that can be easily analyzed. An increase in prednisone dose of less than or equal to 10 mg/day from their prednisone dose at study entry will be permitted during the trial for increased disease activity with a standardized taper allowable in small monthly decrements to the patient's baseline dose or 5 mg/day, whichever is less.

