10.4 Blinding, Packaging, Labeling and Storage

Study agent (15 mg pioglitazone or placebo) will be packaged in identical vials each containing 300 capsules. Both study agents will be blinded using identical-looking capsules prepared by a vetted vendor selected by the NIH Pharmaceutical Development Service (PDS). Each vial will be labeled with a treatment number specific to the subject. A 300 capsule (one vial) supply of study agent will be given to each subject at enrollment at the baseline visit and at month 5. The amount of study agent dispensed will be sufficient to last from baseline to month 3, and from month 5 to month 8. The randomization code will be provided by the Clinical Center Research Pharmacy, as mentioned above. Emergency unblinding will occur in the case of a serious adverse event (SAE) that is considered potentially secondary to the drug. Unblinding will be performed by PDS. Only the pharmacists will be unblinded throughout the trial. The subjects, the investigators, and the study site staff will remain blinded to study medication assignment during the entire study period. Compliance with study treatment and pill counts will be performed by the research nurse/study coordinator and this information will be provided to PDS as well.

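### The barrier-method rule covers only oral contraceptives, although the interaction the protocol states is not limited by route

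*Combined protocol and SAP*

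**What the plan says.** Section 12.2.2.6 (Study Drug) lists the risks of pioglitazone in this non-diabetic population. One bullet reads: "Interaction with hormonal contraceptives may reduce the effectiveness of hormonal contraception". The next sentence gives the precaution: "Patients will be required to also use a barrier method during the trial if they are taking oral contraceptives".

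Section 9.2 item 1 lists the methods that count as adequate contraception for women who could become pregnant, and asks a clinician to document the method. Oral contraceptives qualify only when combined with a condom or diaphragm. "Hormone implants" and "Injectable contraceptives" appear as entries of their own, with no barrier attached. Intrauterine devices are also a separate entry, with no mention of device type. The remaining entries, abstinence and a vasectomized partner, are not hormonal.

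Section 12.1.1 names required contraception and pregnancy testing as the measures that protect women who could become pregnant.

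**The concern.** The risk is worded for hormonal contraception as a class, while the precaution covers one member of that class. The reader cannot tell whether the limit to oral products was a reasoned choice or an oversight.

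The trial enrols mainly women (section 12.1.2.1 expects about 80-90% female participants), and section 12.2.2.6 notes that "all patients will at some point receive pioglitazone given the crossover nature of trial". On the protocol's own premise, a woman relying on an implant or injectable alone would take the study drug with a method that the drug may weaken. Section 12.3.17 gives pioglitazone as pregnancy Category C, without adequate controlled studies in pregnant women. At stake is how well one of the two protections named in section 12.1.1 works. The trial's estimates are not at stake.

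**Working it through.** There is no stated figure to reproduce. The check sets the interaction as worded in 12.2.2.6 against the contraception list in 9.2 item 1. It assumes that injectable contraceptives are hormonal, which the protocol does not spell out.

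| Entry in 9.2 item 1 | Falls under the interaction as worded? | Barrier required? |
|---|---|---|
| Oral contraceptives | Yes | Yes, in both sections |
| Hormone implants | Yes | No |
| Injectables | Yes | No |
| Intrauterine device, type not given | Only if the device is hormonal | No |
| Abstinence; vasectomized partner | No | Not relevant |

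**Count of entries.** Three hormonal methods are named and one carries the barrier rule, which leaves 3 - 1 = 2 without it. If hormonal intrauterine devices are counted, there are four hormonal methods, and 4 - 1 = 3 carry no barrier. These counts locate the gap in the list. They do not measure the number of women affected or the size of any loss of effectiveness.

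**Do other safeguards close the gap?**

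- *Pregnancy tests.* Table 3 schedules one at screening and one with the safety labs at baseline and months 1, 3, 5, 6 and 8, so 1 + 6 = 7 in all. Within each treatment period the longest nominal interval is two months (3 - 1 = 2 in the first, 8 - 6 = 2 in the second). Testing finds a pregnancy after conception and does not prevent it.
- *Stopping rule.* Section 10.1 stops study agent when a participant becomes pregnant. This also acts after conception.
- *Clinician documentation.* Section 9.2 item 1 has a clinician record the method. This is a check before conception, but the list being checked accepts implants and injectables alone, so it adds no barrier.

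**Could the rule be limited to the pioglitazone period?** No. Section 10.4 says: "The subjects, the investigators, and the study site staff will remain blinded to study medication assignment during the entire study period". Nobody at the site knows which period is active, so a barrier rule has to run throughout the trial: 3 months, a washout of about 2 months, and 3 months again, about 8 months in total.

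**The case against.** The strongest reply is that the two sections do not conflict. Both give the same oral-only rule, so sites know what to do, and the second sentence of the bullet may simply mark where the authors judged action to be needed. It is correct that the instructions agree. A reader might infer a contradiction between sections 9.2 and 12.2.2.6, but there is none. What remains is that the agreed rule is narrower than the risk it answers, with no reason given in the supplied text. Consent pages are not in the review copy, so an explanation there cannot be ruled out. The eligibility rule would still be as it stands in 9.2.

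A second reply is that whether implants, injectables or hormonal intrauterine devices are affected depends on route-specific data that the documents do not contain. This stands in full. A reader might infer that women using these methods are in fact less protected, and the documents do not support that. They support only the mismatch between warning and precaution.

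Third, it would go too far to say that hormonal intrauterine devices are left out. The entry is unqualified, so on a plain reading a hormonal device is accepted alone. The protocol simply does not distinguish the types.

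Fourth, the consequences are limited. Pioglitazone exposure is about 3 months per participant, tests are frequent, drug stops on pregnancy, and section 12.3.17 sends a pregnant participant to high-risk obstetrics. The animal findings cited there were at 10 to 40 times the maximum recommended human dose, so fetal harm at the trial dose is not shown. These points reduce the weight of the concern but do not supply the missing barrier or the missing reason.

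**Conclusion.** The point holds as a mismatch inside the protocol: the stated interaction has no route limit, the precaution is limited to oral contraceptives, and no justification appears in the documents supplied. Implants and injectables are clearly outside the barrier rule. Hormonal intrauterine devices are too, on a plain reading.

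The size cannot be expressed in women or pregnancies, because the documents give neither the number of users nor any loss of effectiveness by route. A reader might take two of three, or three of four, methods without a barrier as a measure of risk, but those fractions only count list entries. There is no effect on sample size, power, error rates or analysis. The conclusion rests on reading the warning as written and on treating injectables as hormonal. It is a low-severity participant-safety point and a cheap improvement.

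**What to change.** In section 9.2 item 1, accept hormone implants and injectable contraceptives only together with a barrier method, as already done for oral contraceptives. State that hormonal intrauterine devices follow the same rule unless the sponsor documents that they are unaffected. In section 12.2.2.6, extend the barrier sentence to the same methods and keep its application to the whole trial.

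If the sponsor has route-specific evidence that non-oral methods are unaffected, the better change is to narrow the warning in 12.2.2.6 to oral contraceptives, cite the evidence, and leave the list in 9.2 as it is.

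Either route is a short wording change. The first adds a small burden, a barrier method for about 8 months, for an unknown number of women using these methods. The second adds none. Neither changes visits, sample size or analysis.
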